7.4.2.2 SECONDARY OUTCOME(S)

The first secondary outcome is the rate of COPD exacerbations over the one-year follow-up. This outcome will be based on the number of hospitalizations and on the number of courses of treatment with an oral corticosteroid. A gap of at least 30 days between treatment courses will be required to consider the exacerbations as separate events. The second secondary outcome is the occurrence of the first hospitalization for community-acquired pneumonia (serious pneumonia). Pneumonia will be defined from the following ICD10 codes: J10.0; J11.0; J12-J18; J22; J69; J85.0; J85.1; J86. This definition has been used successfully in COPD [P07-09514; P16-10095].

7.4.3 COVARIATES

Sex, previous treatment and previous acute COPD exacerbation, as well as calendar year of cohort entry, are all matching factors and will thus inherently be accounted for.

Although we will use the high-dimensional approach to identify variables entering the time-conditional propensity score, some key covariates will be highlighted. First, we will identify key lifestyle variables available in the CPRD, known to be risk factors and potential confounders, including the body mass index (BMI), smoking status and excessive alcohol consumption. Missing data for smoking status and BMI will be entered as an additional category in the model. We will also explore the possibility of obtaining blood eosinophils measured in the year prior to cohort entry and will use this information only if complete.

Second, the occurrence of the study outcomes prior to cohort entry will be identified during the one-year baseline period and adjusted for in the analysis if found to be imbalanced between treatment groups after propensity score matching. In particular, COPD exacerbations occurring in the 30 days prior to the study cohort entry date, a marker of COPD exacerbation risk, will be identified separately from those occurring previously during the baseline year. In addition, the severe exacerbations requiring hospitalizations will be counted, while the moderate exacerbations will be identified from counts of prescriptions for oral corticosteroids.

Third, use of other respiratory drugs during the baseline period will be included as a measure of COPD severity. Thus, the number of prescriptions for short-acting beta-agonists, anticholinergics, methylxanthines and muscarinic antagonists used during the year prior to cohort entry will be identified. As well, the number of prescriptions for antibiotics for a respiratory condition will be counted. In addition, we will count the number of prescriptions for the study drugs used during the baseline period. These will be combined into a single variable because of the study design which inherently selects patients into the two study groups according to their prior LABA, TIO or ICS use. Finally, for each of the cohorts, baseline co-morbidity will be measured using diagnoses and prescriptions for various conditions observed often in patients with COPD, namely cardiovascular disease, diabetes, thyroid disease, renal failure, autoimmune disease and cancer, all in the year prior to cohort entry.

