7.7 STUDY SIZE

In our previous study of the cardiovascular effects of long-acting bronchodilators, there were around 230,000 users of LABA or TIO between 2002 and 2012 in the CPRD, which should include around 140,000 who come from HES-linked practices [P16-10095]. From these, we expect around 4,000 who received a LABA and tiotropium on the same day, where the LABA is not combined with an inhaled corticosteroid in a single inhaler. The number of users of LABA-ICS is over 100,000, providing a large pool for matching purposes. Thus, after matching and trimming, we expect the study to include a minimum of 3,000 patients per arm, a conservative estimate. Using recent data from the FLAME trial [P16-05628], we expect that the cumulative incidence of a first COPD exacerbation, moderate or severe,

during the one-year follow-up is expected to be 50%. These sample sizes will permit to detect a 15% reduction in the risk of a first exacerbation (hazard ratio 0.85) with 99% power and a 10% reduction (hazard ratio 0.90) with 97% power. For the severe exacerbations, we expect the one-year cumulative incidence to be around 15%, which will permit to detect a 20% reduction in the risk of a first severe exacerbation (hazard ratio 0.80) with 92% power.

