7.9 DATA ANALYSIS

7.9.1 MAIN ANALYSIS

For the base cohort, patient characteristics at baseline will be described using standard descriptive statistics. The unmatched study cohort, which will also address the tertiary objective, will be used to provide and compare baseline patient characteristics between the two groups. These comparisons will also be provided for the matched cohort.

For the analysis of the primary objective, the matched cohort will be used to estimate the crude 1-year cumulative incidence of severe and moderate COPD exacerbations for the two combination treatment groups. The main comparative analysis will also be based on the matched cohort and a time-dependent Cox proportional hazard regression model to perform an as-treated analysis that assesses the effect of current use of LABA-TIO combination versus the LABA-ICS combination on the risk of a first COPD exacerbation. It will provide an estimate of the hazard ratio (HR) of a COPD exacerbation associated with LABA-TIO use relative to LABA-ICS use, along with 95% confidence intervals (CI). Current use will be defined as a prescription dispensed within the 60-day period of the date defined by the risk set of the Cox model. This approach allows consideration of exposure as time-dependent, accounting for the changes in exposure during the follow-up. In particular, this analysis

censors patients stopping one or both of the drugs prior to the index date. Besides the matching inherent in the design, the Cox proportional hazard regression model will be adjusted for additional confounders. This model will include patient characteristics found to be different after matching on propensity scores, as well as the decile of propensity score. Body mass index (BMI) is expected to be the only variable with missing data in the CPRD, though infrequently (less than 4% of subjects in our previous studies in COPD). Patients with missing BMI will be classified as a separate category.

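### Matching balances its factors at cohort entry only; the as-treated Cox model should condition on them, because arm-specific censoring can unbalance later risk sets

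*Combined protocol and SAP*

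**What the plan says.** Section 7.3 matches each LABA-TIO initiator to a LABA-ICS initiator exactly on sex, previous component of treatment and exacerbation in the prior year, within calendar-year exposure sets, and then on the time-conditional propensity score. Section 7.4.3 concludes that sex, previous treatment, previous exacerbation and calendar year of cohort entry "are all matching factors and will thus inherently be accounted for".

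Section 7.9.1 describes the main analysis as an as-treated, time-dependent Cox model that "censors patients stopping one or both of the drugs". Section 7.3 adds a different censoring trigger in each arm: an ICS for LABA-TIO, tiotropium for LABA-ICS. On covariates, 7.9.1 presents adjustment as additional to the matching: "This model will include patient characteristics found to be different after matching on propensity scores, as well as the decile of propensity score". The pneumonia Cox model is described as similar, and the negative binomial model takes the same approach to covariates.

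No visible passage says whether the Cox model is stratified on the matched set, mentions censoring weights, or gives expected rates of stopping, switching or adding.

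**The concern.** Exact matching makes the two arms alike on these factors at day 0. A Cox model compares the arms among those still at risk at each later event time. If, say, patients with a prior exacerbation leave one arm faster than the other, the remaining patients differ in risk and the hazard ratio moves without any drug effect.

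The covariate rule does not protect against this. It admits characteristics that differ after matching, and an exactly matched factor does not differ then. The factors that the plan thought important enough to match on are thus the ones its rule would not bring into the model. What is at stake is the primary hazard ratio, and by the same route the pneumonia hazard ratio and the exacerbation rate ratio.

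**Working it through.** **The plan's own figures.** Section 7.7 expects 3,000 per arm ("we expect the study to include a minimum of 3,000 patients per arm, a conservative estimate") and a 50% one-year incidence of a first exacerbation. The two-proportion formula, power = Φ(|p1 − p2| / √{[p1(1 − p1) + p2(1 − p2)]/n} − 1.96), gives:
- 0.50 v 0.425: 0.9999 (stated 99%)
- 0.50 v 0.45: 0.05/0.01288 = 3.88, so 0.973 (stated 97%)
- 0.15 v 0.12: 0.03/0.00881 = 3.40, so 0.925 (stated 92%)

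The stated powers reproduce, so these inputs are used below. Two-sided 5% is assumed; 7.7 states no alpha, and 7.9.1 plans 95% intervals. The formula treats the ratios as risk ratios, which is a separate matter.

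**How the displacement arises.** Take one exactly matched binary factor X with prevalence p and hazard ratio θ, and no drug effect. With S the event-free and G the uncensored probability, the share of X = 1 still at risk in arm a is

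p S₁ Gₐ₁ / (p S₁ Gₐ₁ + (1 − p) S₀ Gₐ₀),

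and the hazard ratio at that time is (1 + (θ − 1) × share in LABA-TIO) / (1 + (θ − 1) × share in LABA-ICS).

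**Example by hand (p = 0.5, θ = 2).** A 50% overall incidence requires S₀ = 0.618 and S₁ = 0.382 at one year. Assume that 20% of X = 0 patients are censored in both arms, and of X = 1 patients 60% in LABA-TIO and 30% in LABA-ICS.
- LABA-TIO share: 0.382 × 0.4 = 0.153; 0.618 × 0.8 = 0.494; 0.153/0.647 = 0.236.
- LABA-ICS share: 0.382 × 0.7 = 0.267; 0.267/(0.267 + 0.494) = 0.351.
- Hazard ratio at one year: 1.236/1.351 = 0.915. At entry it is 1. The Cox average over the year is 0.963.

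**Simulation.** 300 studies per row, 3,000 matched pairs, true hazard ratio 1, p = 0.5. Censoring is the assumed one-year probability for X = 0 / X = 1, with exponential times unless day 60 is stated.

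| LABA-TIO v LABA-ICS | θ | HR without X | Rejection | HR with X | Rejection |
|---|---|---|---|---|---|
| none | 2 | 1.00 | 5% | 1.00 | 5% |
| 30/70 v 30/70 | 2 | 1.00 | 5% | 1.00 | 6% |
| 60/60 v 30/30 | 2 | 1.00 | 3% | 1.00 | 3% |
| 30/50 v 30/30 | 2 | 0.98 | 8% | 1.00 | 5% |
| 20/60 v 20/30 | 2 | 0.96 | 14% | 1.00 | 6% |
| 20/60 v 20/30, day 60 | 2 | 0.94 | 32% | 1.00 | 5% |
| 20/80 v 20/20 | 2 | 0.91 | 61% | 1.00 | 6% |
| 20/80 v 20/20, day 60 | 2 | 0.87 | 88% | 1.00 | 5% |
| 20/80 v 20/20 | 3 | 0.87 | 94% | 1.00 | 4% |
| 20/30 v 20/60 | 2 | 1.04 | 15% | 1.00 | 3% |
| 20/20 v 20/80 | 2 | 1.09 | 56% | 1.00 | 5% |

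Stratifying by matched pair also returned 1.00 throughout. With p = 0.3, the fourth, fifth and seventh rows have limiting values of 0.98, 0.97 and 0.94.

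**A second parameterisation.** Event hazard 0.5 × 2^X and background censoring hazard 1 per year, with X = 1 patients in LABA-TIO censored 1.5, 2 or 3 times as fast: 0.97, about 0.95 and about 0.91. Stratified on X: 1.00 to 1.01. The threefold case means 1 − e⁻³ = 95% censored in a year, against 1 − e⁻¹ = 63% in the other groups.

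**Size against the design.** ln 0.963 = −0.038 and ln 0.90 = −0.105, so the by-hand case displaces the estimate by 0.038/0.105 = 36% of the smaller effect for which 7.7 gives power. With about 2,489 events the standard error is 2/√2489 = 0.040, so the shift is just under one standard error. That is consistent with rejection near 15%.

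**The case against.** **The plan does not exclude the matching factors.** Correct: that they stay out is an inference from the covariate rule. A pair-stratified model would preserve the matching, and 7.9.1 neither promises nor rules it out. The table of contents and the checklist also point to analysis text on page 21 that is not visible, so the statement is limited to what can be read.

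**Other adjustment may carry the same information.** Section 7.9.1 always includes the propensity score decile. Section 7.6 says that severity, comorbidity and concomitant drugs are adjusted for in the outcome model. These may recover part of the imbalance, and the simulations, with one factor and no other covariate, show the effect without that help. But none of these passages guarantees conditioning on the matching factors themselves.

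**Calendar year may not be exactly balanced.** Section 7.3 forms exposure sets by year of entry into the base cohort, while 7.4.3 names year of cohort entry. The latter could differ after matching and so enter the model. This stands for year, not for sex, previous treatment or prior exacerbation.

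**Stronger readings.** A reader might infer that as-treated censoring by itself undoes the matching. It does not: censoring that depends on arm alone, or on the factor alike in both arms, leaves 1.00. A reader might also infer a bias well below 1 in favour of LABA-TIO. The documents give no switching rates and so fix no direction: faster exit of high-risk LABA-ICS patients pushes the ratio above 1. Nor do they rank prior exacerbation above the other matching factors as a predictor.

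**Conclusion.** The claim in 7.4.3 holds at entry but is too strong for the as-treated analysis. Displacement requires two things together: a matching factor that predicts the outcome, and censoring that depends on it differently in the two arms. The different triggers in 7.3 make the second possible, but nothing in the documents shows that it occurs.

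If both hold, a null hazard ratio moves to about 0.94 to 0.98 for moderate assumed differences (false rejection 8 to 32%). It reaches about 0.91 or lower only for large ones, such as 80% v 20% one-year censoring of high-risk patients. Mirror-image values above 1 are equally possible. All censoring rates, prevalences and factor effects are assumptions. Conditioning on the factor restored about 1.00 in every scenario, provided that censoring depends only on arm and the matching factors. The change should be made: it is nearly free and uses data already planned for collection.

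**What to change.** - **7.9.1, Cox models (exacerbation and pneumonia):** stratify the baseline hazard on, or include as covariates, sex, previous treatment, prior exacerbation and calendar year of entry, regardless of baseline balance. State whether matched sets are used in the model.
- **7.9.1, negative binomial model:** include the same factors as covariates.
- **Reporting:** tabulate censoring by reason, arm and matching factor.
- **7.4.3:** replace the clause "are all matching factors and will thus inherently be accounted for" with *are balanced at entry and conditioned on in the outcome models*. Make 7.3 and 7.4.3 name the same calendar year.
- **Sensitivity analysis:** baseline conditioning does not deal with censoring driven by post-entry events. Add an analysis with inverse-probability-of-censoring weights for that.

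Cost: SAP wording and a few model terms. Full cross-stratification gives up to 2 × 4 × 2 × 14 = 224 strata and raises the standard error by about 2 to 5%; covariate adjustment costs less. Stratifying by matched pair also removes the displacement, but raised the standard error by about 30% when background censoring was one per year, so it is the dearer option.

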7.5 DATA SOURCES

The Clinical Practice Research Datalink (CPRD) will be used for this study. It includes computerized medical records of more than 12 million patients from more than 650 general practices in the United Kingdom. General practitioners, using standardized recording of medical information, record data on the patient's demographic characteristics, symptoms, history, medical diagnoses, and drug prescriptions, as well as details of referrals to specialists and hospitals. The completeness and validity of the recorded information on diagnoses, coded using READ codes, and drug exposures, coded using a coding system with a direct mapping to the NHS dictionary of medicines and devices, are checked on an ongoing basis by staff of the CPRD and have been shown in several studies [R11-2162; R16-2198]. In addition, the CPRD can be linked by unique identifier to the Hospital Episodes Statistics (HES) database which provides extensive information on all hospitalizations, coded using ICD-10 codes, including data on length of stay, ward types, as well as extensive disease and procedure coding, based on OPCS4 (Office of Population Censuses and Surveys Classification of Interventions and Procedures) codes. The linkage between the CPRD and the HES databases applies to over half of the practices contributing to the CPRD. The database has been used for the study of numerous diseases, including studies of COPD [R16-2197; P16-10095].

7.6 BIAS

Several potential biases inherent to any observational study need to be considered. First, confounding by indication could be an issue. Matching subjects initiating LABA-TIO with subjects initiating LABA-ICS on several marker of disease, including prior COPD exacerbations, previous treatment and on the propensity score should limit this potential bias since matched subjects will have comparable probability of using either combination. In addition to matching on the propensity score, sex, prior exacerbation, prior treatment and calendar time, several variables such as general severity of COPD, comorbidity and concomitant drug use will be in the propensity score and adjusted for in the outcome model. Second, there is the possibility of information bias due to misclassification of the outcomes or exposure. CPRD contains prescriptions written by the GP rather than filled or taken by patients. This could be a source of misclassification of exposure. Another source of information bias due to the presence of hospitalizations during follow-up, particularly during the current exposure window, where GP prescriptions are not available, so that exposure is not measurable. Finally, the linkage to HES data to identify hospitalization for COPD exacerbation and for community-acquired pneumonia should reduce the potential for misclassification of outcomes.

7.7 STUDY SIZE

In our previous study of the cardiovascular effects of long-acting bronchodilators, there were around 230,000 users of LABA or TIO between 2002 and 2012 in the CPRD, which should include around 140,000 who come from HES-linked practices [P16-10095]. From these, we expect around 4,000 who received a LABA and tiotropium on the same day, where the LABA is not combined with an inhaled corticosteroid in a single inhaler. The number of users of LABA-ICS is over 100,000, providing a large pool for matching purposes. Thus, after matching and trimming, we expect the study to include a minimum of 3,000 patients per arm, a conservative estimate. Using recent data from the FLAME trial [P16-05628], we expect that the cumulative incidence of a first COPD exacerbation, moderate or severe,

during the one-year follow-up is expected to be 50%. These sample sizes will permit to detect a 15% reduction in the risk of a first exacerbation (hazard ratio 0.85) with 99% power and a 10% reduction (hazard ratio 0.90) with 97% power. For the severe exacerbations, we expect the one-year cumulative incidence to be around 15%, which will permit to detect a 20% reduction in the risk of a first severe exacerbation (hazard ratio 0.80) with 92% power.

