Study data source:	
United Kingdom's Clinical Practice Research Datalink (CPRD) linked with the Hospital Episodes Statistics (HES) database
		
Expected study size:	
New users of LABA and tiotropium : 3,000
 
New users of LABA and ICS: 3,000
		
Main criteria for inclusion:	
 - New users of long-acting bronchodilators, LABA and tiotropium on the same date or of LABA and ICS, either as a fixed-dose combination or free combination, on the same date between January 2002 and December 2015. - Diagnosis of COPD and age \geq 55 years 		

Name of company: Boehringer Ingelheim		 Boehringer Ingelheim	
Name of product: Spiriva			
Name of active ingredient: Tiotropium bromide			
Protocol date: 19 May 2017	Study number: 0205-0538	Version/Revision: 1.1	Version/Revision date: Version 1.1, May 19, 2017

Proprietary confidential information © 2017 Boehringer Ingelheim International GmbH or one or more of its affiliated companies. All rights reserved. This document may not - in full or in part - be passed on, reproduced, published or otherwise used without prior written permission
			
Main criteria for exclusion:	-Less than one year of medical history information prior to the date of combined treatment initiation (cohort entry) -Asthma diagnosis		
Comparison groups:	Initiating LABA and tiotropium compared to initiating LABA and ICS therapy		
Expected duration of exposure:	One year for the primary and secondary analyses		

TABLE OF CONTENTS

TITLE PAGE	1
PROTOCOL ABSTRACT	3
TABLE OF CONTENTS	6
LIST OF TABLES	8
LIST OF FIGURES	9
1. LIST OF ABBREVIATIONS AND TERMS	10
2. RESPONSIBLE PARTIES	11
3. AMENDMENTS AND UPDATES	12
4. MILESTONES	13
5. RATIONALE AND BACKGROUND	14
6. RESEARCH QUESTIONS AND OBJECTIVES	15
7. RESEARCH METHODS	16
7.1 STUDY DESIGN.....	16
7.2 SETTING.....	16
7.3 SUBJECTS	16
7.4 VARIABLES	17
7.4.1 EXPOSURES.....	17
7.4.2 OUTCOME(S).....	17
7.4.2.1 PRIMARY OUTCOME(S).....	17
7.4.2.2 SECONDARY OUTCOME(S).....	18
.....	18
7.4.3 COVARIATES.....	18
7.5 DATA SOURCES	19
7.6 BIAS	19
7.7 STUDY SIZE	19
7.8 DATA MANAGEMENT	20
7.9 DATA ANALYSIS	20
7.9.1 MAIN ANALYSIS	20
.....	21
7.10 QUALITY CONTROL.....	22
7.11 LIMITATIONS OF THE RESEARCH METHODS	22
7.12 OTHER ASPECTS	22
8. PROTECTION OF HUMAN SUBJECTS	23
9. MANAGEMENT AND REPORTING OF ADVERSE EVENTS/ADVERSE REACTIONS.....	24
10. PLANS FOR DISSEMINATING AND COMMUNICATING STUDY RESULTS	25
11. REFERENCES.....	26

11.1	PUBLISHED REFERENCES.....	26

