The study cohort will be formed from the base cohort using an incident new-user cohort design with time-conditional propensity scores [P17-04653]. We will thus identify from the base cohort all subjects who, during follow-up, received for the first time prescriptions for a LABA and a tiotropium on the same day, but no inhaled corticosteroid. This can occur as the first time they received a long-acting bronchodilator, with both a LABA and tiotropium as initial treatment, or with initial treatment with a single long-acting bronchodilator followed by the addition of the other long-acting bronchodilator. We will then identify from the base cohort all subjects who, during follow-up, received for the first time prescriptions for a LABA and an ICS on the same day, as two different prescriptions or in a single inhaler, but no tiotropium. Here again, this can occur as the first time they received a LABA and ICS as initial treatment, or with initial treatment with a LABA followed by the addition of ICS or vice versa. Cohort entry will be taken as the first date that LABA and tiotropium or LABA and ICS prescriptions are given simultaneously. All subjects will require at least one year of up-to-standard (UTS) medical history prior to study cohort entry to allow a baseline period for the covariates and identification of new use. New use will thus be defined as the first simultaneous prescriptions for LABA and tiotropium or for LABA and ICS, preceded by prescriptions for only one of the two drug classes or none in the baseline year.

To form the study cohort, we will identify, for each subject initiating LABA and tiotropium (LABA-TIO) treatment, a matched LABA-ICS comparator subject using a time-conditional

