propensity score-matched approach. The potential comparator subjects will be selected from the base cohort by forming time-based exposure sets defined by the calendar year of entry into the base cohort for the LABA-TIO and LABA-ICS simultaneous prescription users. To allow matching on the propensity of treatment choice, we will compute high-dimensional time-conditional propensity scores (TCPS) by identifying all available data (e.g., diagnoses, procedures, medications) in the one-year period prior to the date of cohort entry for each time-based exposure set using Cox proportional hazards regression. Then, for each LABA-TIO exposed subject, and starting chronologically with the first one, we will identify a matched comparator subject from the members of the subject's time-based exposure set. We will first match subjects on sex, previous components of the study treatment (LABA only, TIO only, ICS alone, none of these) and the presence of an acute COPD exacerbation in the year before cohort entry. The matched reference subject will then be selected as the one with the closest time-conditional propensity score in the matched set, after trimming within each exposure set, and allowing a maximum difference in scores of 0.05 for a match. In the absence of a tight propensity score match, we will take the closest and the analysis will be complemented by an adjustment for the propensity score.

After matching, the subjects in the study cohort will be followed up for up to one year from cohort entry (the date of the matched set), with follow-up ending at the earliest of the date of a switch or addition of either an ICS for the LABA-TIO group or of tiotropium to the LABA-ICS group, death, one year after cohort entry, December 31, 2016, or the end of coverage in the practice, whichever occurs first.

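### Drawing one LABA-ICS comparator per LABA-TIO patient gives about 81% power at a hazard ratio of 0.90, not the stated 97%; a variable ratio of up to 1:4 would recover part of the shortfall.

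*Combined protocol and SAP*

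**What the plan says.** Section 7.3 identifies for each LABA-TIO initiator "a matched LABA-ICS comparator subject using a time-conditional" propensity score. Candidates share the calendar-year exposure set and are matched exactly on sex, prior treatment component and an exacerbation in the year before entry. From these, "The matched reference subject will then be selected as the one with the closest time-conditional propensity score in the matched set", after trimming and "allowing a maximum difference in scores of 0.05 for a match". If there is no tight match, the closest subject is taken and the analysis is adjusted for the score.

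On numbers, section 7.7 says "we expect around 4,000 who received a LABA and tiotropium on the same day" (with the LABA not in a fixed inhaler with ICS), and "The number of users of LABA-ICS is over 100,000, providing a large pool for matching purposes". It expects at least 3,000 per arm after matching and trimming. The abstract lists "New users of LABA and ICS: 3,000" beside the same number for LABA and tiotropium.

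Section 7.7 claims 99% power at a hazard ratio of 0.85 and 97% at 0.90 (50% incidence), and 92% at 0.80 for severe exacerbations (15% incidence). Section 7.9.1 estimates the primary hazard ratio in the matched cohort with an as-treated Cox model adjusted for propensity-score decile, and treats pneumonia similarly. No reason is given for a 1:1 ratio, and no pneumonia incidence or power is given.

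**The concern.** LABA-TIO is the scarce group and its size is fixed by prescribing history. The number of comparators is a choice, and the protocol itself describes the comparator pool as large. At 1:1, sampling error among comparators makes up about 48% of the variance of the log hazard ratio. That is the part the sponsor can reduce from data already held.

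The power statement hides the need for it. A reader of section 7.7 would think that 3,000 per arm leaves a wide margin at a hazard ratio of 0.90. For the planned model it does not, and as-treated censoring reduces the power further. Pneumonia, which section 5 sets as the safety counterweight to effectiveness, will have fewer events and carries no power statement.

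**Working it through.** **Inputs.** From the documents: 3,000 LABA-TIO patients, 50% and 15% one-year incidence, hazard ratios 0.90 and 0.80 (section 7.7), and one comparator each (section 7.3). Assumed: two-sided 5%, since section 7.7 gives no alpha but section 7.9.1 reports 95% intervals; the stated incidences apply to LABA-ICS; complete follow-up unless noted.

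**1. Reproducing the stated power.** Apply the hazard ratio as a risk ratio and compare two proportions with 3,000 per arm:
- 50% v 45%: SE = √[(0.2500 + 0.2475)/3,000] = 0.01288; 0.05/0.01288 − 1.96 = 1.92; power 97%.
- 15% v 12%: SE = √[(0.1275 + 0.1056)/3,000] = 0.00881; 0.03/0.00881 − 1.96 = 1.44; power about 92.5%.
- 50% v 42.5%: above 99.9%.

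These agree with the stated 97%, 92% and 99%. But 50% v 45% corresponds to a hazard ratio of ln 0.55 / ln 0.50 = 0.86, not 0.90.

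**2. Power for the planned Cox model.** Var(log HR) = 1/d1 + 1/d0, with d1 = 3,000 × (1 − 0.5^0.9) = 1,392 and d0 = 1,500 × k for k comparators each. Power = Φ(|ln 0.90|/SE − 1.96), with |ln 0.90| = 0.1054.

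| Ratio | d0 | SE | SE v 1:1 | Power |
|---|---|---|---|---|
| 1:1 | 1,500 | 0.0372 | – | 81% |
| 1:2 | 3,000 | 0.0324 | 13% smaller | 90% |
| 1:4 | 6,000 | 0.0297 | 20% smaller | 94% |

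Schoenfeld's formula gives 81%, 91% and 95%. At a hazard ratio of 0.85 and 1:1, power is 99%, as stated.

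Severe events, hazard ratio 0.80: d1 = 3,000 × (1 − 0.85^0.8) = 366 and d0 = 450; SE = 0.0704; power 89% at 1:1, against the stated 92%. At 1:4 it is 97%.

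**3. As-treated censoring.** The documents do not give the share of events retained. At a hazard ratio of 0.90, moving from 1:1 to 1:4 changes power from 66% to 84% if 70% of events remain, from 59% to 78% at 60%, and from 52% to 71% at 50%.

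**4. Pneumonia.** Incidence is assumed, since none is given. At 2%, 5% and 8% with a hazard ratio of 0.80, the SE falls from 0.194, 0.122 and 0.097 at 1:1 to 0.158, 0.100 and 0.079 at 1:4, about 18% in each case.

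**5. Supply.** For 3,000 patients, 1:2 needs 6,000 comparators and 1:4 needs 12,000, which is 6% and 12% of the 100,000 users.

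**6. An uneven ratio.** Suppose one third of the LABA-TIO patients can be matched only 1:1 and two thirds reach 1:4 (assumed). With weights of 1/k, the effective number of comparators is 3,000² / (1,000 + 2,000/4) = 6,000. That is equivalent to 1:2, so power is about 90%.

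**7. Stratifying by matched set.** A set stops contributing once its LABA-TIO member, or all its comparators, have had an event or been censored. Simulating the mixed ratio in step 6 with a set-stratified Cox model gives about 89% with complete follow-up. At two levels of as-treated stopping, at which the unstratified 1:1 model has 68% and 52%, it gives about 66% and 46%. The exact figures depend on the assumed stopping pattern, and lighter stopping can leave a small gain, but most of the benefit is lost.

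**8. Upper bound.** Near a hazard ratio of 1, unlimited comparators halve the variance, so the SE falls by at most 1 − 1/√2 = 29%.

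**The case against.** The strongest objection is that section 7.11 ranks confounding by indication among the most important threats, and a single closest match is a defensible way to favour comparability over precision. This stands in part. Later comparators will be somewhat less close, and forcing a fixed ratio could harm balance. It does not rule out extra comparators that meet the same exact factors and the 0.05 limit.

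Supply will also be uneven. Section 6 names tiotropium users who add a LABA as an entry route to LABA-TIO. The LABA-ICS routes described in section 7.3 run through LABA or ICS, so comparators with prior tiotropium only may be few. Section 7.3 already foresees missing tight matches. This stands, and is why the ratio must be variable.

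The figure of 3,000 per arm is a stated minimum. If all 4,000 LABA-TIO starters were matched, 1:1 would give SE 0.0322 and about 90% power, still short of 97%.

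A reader might infer that more than 95% of eligible comparators are thrown away, or that about 25 are available per patient. The documents do not support this. Section 7.7 counts users, and does not say that the COPD, age, asthma, history, first-simultaneous-prescription and no-tiotropium conditions have been applied. A reader might also blame the 1:1 ratio for the gap between 97% and 81%. The gap comes from reading the hazard ratio as a risk ratio, and 1:4 does not close it.

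**Conclusion.** The point holds as a loss of efficiency together with an incorrect power figure. Nothing here shows bias in the planned estimate. On the protocol's own inputs, and assuming two-sided 5% and complete follow-up, power at a hazard ratio of 0.90 is about 81% at 1:1 and not 97%; for severe events at 0.80 it is about 89% and not 92%. An average of 1:2 would give about 90% for the primary outcome, and 1:4 about 94%. The realistic gain lies between the 1:1 and 1:4 figures, depending on how many strata are thin. It rests on at least 6,000 to 12,000 eligible LABA-ICS initiators, which is plausible from the stated pool but not confirmed. It also depends on leaving the Cox model unstratified by matched set. The pneumonia gain is of similar relative size, but its absolute precision depends on an incidence that the plan does not give.

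**What to change.** 1. **Section 7.7:** restate power at a hazard ratio of 0.90 as about 81%, and for severe events at 0.80 as about 89%, if 1:1 is kept; otherwise give the values for the ratio adopted. Say that as-treated censoring lowers them further, and state the alpha and the event share assumed.

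2. **Section 7.3:** complete a first match for every LABA-TIO patient under the current rule. Then add up to three more comparators per patient that meet the same exact factors and the 0.05 limit, with no closest-subject fallback for these. Doing all first matches first stops early patients from using up the only close match of later ones.

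3. **Section 7.9.1:** keep the Cox model adjusted for propensity-score decile, add the matching factors, and do not stratify by matched set. Weight each comparator by one over the number in its set, and use a robust variance clustered on the set. Use the same weights in the negative binomial model.

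The cost is protocol wording and a small programming change; no patient is recruited and no new data are needed. Later comparators will be slightly less close, so balance should be reported for the weighted cohort. Thin strata, such as prior tiotropium only, will stay near 1:1.
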